5.4 Provision of PrEP

Enrolled participants will be provided with PrEP in the form of daily oral FTC/TDF, dispensed in 30-pill bottles. Participants will be instructed to take one pill orally once

daily with or without food. The drug will be provided to ensure enough study drug until the next visit. A minimum of 2 bottles will be dispensed at the enrollment visit, and 1-2 bottles at follow-up visits to ensure the participant has adequate supply until the next study visit, accounting for potential missed visits and rescheduling. If participants experience difficulties in accessing PrEP for use after study participation due to insurance issues or lack of a health care provider willing to prescribe PrEP, PrEP medication may be provided to participants for an additional 3 months (3 bottles) to ensure continued access to PrEP in the post-study period.

5.5 Study Product Formulation, Content, and Storage

FTC/TDF is a fixed dose combination tablet containing 200 mg of emtricitabine (FTC) and 300 mg of tenofovir disoproxil fumarate (TDF) in each tablet. FTC/TDF study tablets must be stored at 25°C, with excursions permitted to 15°C-30°C (59°F-86°F) (see USP Controlled Room Temperature). FTC/TDF tablets must be stored in the original container while at the site or site pharmacy. Each container is packaged with a child-resistant screw cap and contains a silica gel to protect the product from humidity.

FTC/TDF 200mg/300mg is available as Truvada®, a medication approved by the U.S. Food and Drug Administration (FDA) for treatment of HIV-1 infection and for PrEP to reduce the risk of sexually acquired HIV-1 in adults at high risk. Further information on Truvada® is available in the current package insert, which is located at http://rsc.tech-res.com/safetyandpharmacovigilance.

5.6 Study Product Supply and Accountability

Truvada[®] is manufactured and provided by Gilead Sciences, Inc. Truvada[®] will be shipped directly to the site per the Site-Specific Protocol (SSP). Sites will dispense study medication, either directly or through a site pharmacist, as described in their SSP. Procedures for storage and destruction of unused study products are described in the SSP.

5.7 Study procedures

An overview of the study visits and procedures schedule is presented in Table 1. Presented below is additional information on visit-specific study procedures. At all visits, locator information will be confirmed, and participants will be provided risk reduction counseling, condoms, and lubricant, and a stipend. At all visits, study staff will work with participants to establish continued access to PrEP after completion of the 24-week study; PrEP will be provided to participants for the duration of the study. Beginning at the enrollment visit, study staff will assist participants with PrEP navigation services, including referrals to local PrEP providers/clinics and linkage to PrEP navigators who can help evaluate insurance eligibility, facilitate coverage for PrEP medication and services, and assist with Truvada[®] medication and co-pay assistance programs, with the goal of having participants establish a source for ongoing Truvada medication by the end of the study.

Table 1: Study visits and procedures

	SCR&	ENR	Week 6	Week 12	Week 18	Week 24
Obtain informed consent						
Obtain demographic, risk data, cell phone						
compatibility for assessment of eligibility						
Locator information						
Risk reduction counseling, provide condoms and lube						
HIV 4 th gen						
Creatinine, RPR						
Blood test: HbSAg						
HIV testing according to HIV testing algorithm in SSP						
Oral, rectal swabs for GC, CT						
Urine for GC, CT						
Medical history, limited physical examination†				*		*
Confirm eligibility criteria met						
Randomization						
Download app, provide instructions		I				
Dispense TDF/FTC			*		*	*
Observe first dose using DOT (clinic staff) and DOT		1				
Diary (app)						
Provide PrEP Basics, adherence counseling						
Assist with PrEP and benefits navigation						
CASI: sexual behavior (baseline, week 12 and 24),						
DOT Diary use and acceptability (weeks 12 and 24)						
DBS collection			\checkmark			
DOT Diary exit qualitative interview [¥]						
Provide stipend	\checkmark		\checkmark	\checkmark	\checkmark	

[&]Screening visit must occur within 4 weeks of the enrollment visit

†Medical history and physical exam may be performed at screening and updated at enrollment per site preference

*if indicated

[¥]In a subset of participants

I = immediate intervention arm only

5.6.1 Screening Visit

Participants who express interest in participating in the study will be pre-screened by telephone or online, according to what is allowed at each site, to avoid unnecessary screening visits. The study will be briefly described in a pre-screening call or online, and those participants who remain interested will be scheduled for an in-person screening visit.

At the screening visit, study staff will verify that participants meet the eligibility criteria outlined above. All screening procedures will take place in a private room. Staff will review the informed consent form, including study purpose and design, to ensure that the potential volunteer understands the study and wants to participate. Staff will also review the AiCure Mobile App Authorization Form and offer a printed copy to all participants (this document is located in the DOT Diary app as well). Participants will then be asked to undergo a test of understanding to ensure that they understand the goals of the study, and understand the app and privacy safeguards. Participants who are eligible and demonstrate good understanding of the study may then be screened for the study, after signing the consent form. If the participant answers multiple questions on the test of understanding incorrectly, and is not able to explain the correct answers after additional counseling, the staff may elect to either decline to proceed with screening the participant, or ask the participant to return for an additional screening visit. If upon re-taking the test of

understanding at the follow-up visit, the participant still has multiple incorrectly answered questions, the participant will not be allowed to enroll.

After signing the informed consent, staff will ask the participant to complete a form collecting comprehensive locator information. The participant's blood will be drawn for HIV testing, creatinine, RPR, and hepatitis B surface antigen (HBsAg) testing. Urine and rectal/pharyngeal swabs will be collected for STI testing. Participants will also be provided risk reduction counseling, condoms, and lubricant. The participant will be provided a stipend for completion of screening procedures.

5.6.2 Enrollment visit

Participants who are eligible after screening will return to the clinic for an enrollment visit. All screening procedures must be complete within 4 weeks (28 days) of the enrollment visit. At the enrollment visit, HIV testing will be performed according to HIV testing algorithm in SSP. Participants will complete an online questionnaire via computer-assisted self-interview (CASI) that gathers data on baseline demographics, drug use and sexual behaviors, knowledge and use of PrEP, and experience using technology. Participants will also be provided risk reduction counseling, condoms, and lubricant. A study clinician will then perform a medical history and limited physical exam (this may be done at screening and updated at enrollment, based on site preference). Study staff will confirm participant eligibility and enroll the participant into the study.

Participants will then be randomized to receive the DOT Diary intervention immediately at enrollment (intervention arm) or PrEP alone (control arm) in a 2:1 ratio (see randomization procedures in Section 5.3). Participants who are randomized will be considered enrolled in the study. Participants in the intervention arm will be provided instructions to download the app on to their smartphone. Study staff will demonstrate how to use the DOT Diary app, and participants will complete the tutorial in the app and demonstrate taking their first dose of TDF/FTC using the app. Participants will also select a daily dosing time, and the app will be programmed to send the participant a daily text message or app notification at this time to take their pill and use the app. Participants will also set preferences regarding the sexual diary, including preferences regarding partner rating items. Staff will instruct participants to not include any personally identifiable information about partners in the sexual diary, such as real names or contact information. Staff will emphasize that partner nicknames should be used that help the participant identify the partner but are not easily identifiable to anyone else. For example, "Bob" or "Leather pants guy."

All participants will be dispensed 3 bottles of TDF/FTC (90 pills) and provided the PrEP Basics handout and adherence counseling regarding importance of daily adherence to PrEP for maximal protection and strategies to integrate pill-taking into one's routine. The participant will be provided a stipend for completion of the enrollment visit.

All participants will receive a phone call check-in one week after PrEP initiation to inquire about any side effects or other problems experienced in taking PrEP and provide additional support, if appropriate. Staff will also ask all immediate intervention arm participants about any issues with using the DOT Diary app and provide assistance as needed.

5.6.3 Weeks 6 and 18

At the week 6 and 18 visits, participants will have HIV 4th generation testing and risk reduction counseling performed and their blood collected for DBS. Additional bottles of study drug will be distributed as needed to ensure the participant has adequate supply until the next study visit, accounting for potential missed visits and rescheduling. Participants who are using the app will be asked about any problems or issues with using the app and will provide assistance as needed.

Between all follow-up visits, study staff will reach out to participants by phone or text message in the event of prolonged non-use, multiple overrides of the device, or evidence of suspicious behavior per the *DOT Diary Panel Management and Participant Contact SOP*.

5.6.4 Weeks 12 and 24

In addition to the procedures described at the week 6 and week 18 visits, participants will have blood tests for creatinine, and RPR, as well as urine and oral and rectal swabs for GC/CT at the week 12 and 24 visits. Participants who test positive for STIs will be offered or referred for treatment per local clinic protocol; local guidelines for STI reporting will be followed. They will also complete a CASI assessing sexual and drug use behavior, use of the various components of DOT Diary and acceptability of the app (if they used the app in the past 12 weeks).

At week 12, participants will be dispensed 3 bottles of TDF/FTC (90 pills).

At week 24, up to 24 participants (12 at each site) will complete an exit in-depth interview with a member of the DOT Diary team trained in qualitative methods. The purpose of this interview is to elicit feedback from the intervention arm on their experiences using the app, acceptability and ease of use, any technical difficulties encountered, and how the app could be further improved. Participants will also be asked whether they thought data in the app accurately represents their pill-taking and sexual behaviors, as well as willingness to use the app in future studies of PrEP. Participants in both arms will be asked about their experiences adhering to PrEP, and what might have been helpful in ongoing adherence. Participants will be selected for interviews using purposive sampling based on level of engagement with the app, level of adherence as measured by the app, and to achieve diversity based on sociodemographics (e.g. age, race/ethnicity) and other characteristics. Interviews may also be conducted with control arm participants to learn what would have helped them in taking PrEP. Qualitative interviews may be conducted in-person or via video or phone to facilitate scheduling. All qualitative interviews will be audio-taped; portions or whole interviews may be transcribed if they are particularly informative.

As this is the final clinic visit, the participant will be thanked for his participation, and a notation will be made on whether he is interested in contact for future studies. If the participant has not yet established outside access to PrEP, study staff may dispense an additional 3 bottles of TDF/FTC to minimize gaps in PrEP coverage while they assist the participant in securing ongoing access to PrEP.

For the intervention arm, staff will instruct the participant to uninstall the DOT Diary app from their mobile device to remove any possibility of further data transmission. Staff will assist participants, as needed, in uninstalling the app.

After completion of the study, staff will also be asked to comment on how well the stafffacing interface worked for their interactions with participants, including suggestions for improving the interface or app.

5.6.5. 3-Month Post Study Check In

Participants will receive a phone call check-in three months after completion of in-person study visits to confirm whether they have been able to access PrEP outside of the study. Study staff will provide additional PrEP navigation as needed to connect participants to a local PrEP provider.

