4.5 Participant Retention

Once a participant enrolls in the DOT Diary Longitudinal Pilot, the study site will make every effort to retain him for the entire follow-up period in order to minimize possible bias associated with loss-to-follow-up. Study site staff are responsible for developing and implementing standard operating procedures (SOPs) that reflect retention strategies necessary to achieve the retention goal of 90% at the final study assessment/visit. Components of such procedures may include:

- Thorough explanation of the study visit schedule and procedural requirements during the informed consent process and re-emphasis at each study visit.
- Collection of detailed locator information at the study Screening Visit and updating of this information at each subsequent visit, if necessary.
- Use of appropriate and timely visit-reminder mechanisms.
- Immediate and multifaceted follow-up for missed visits.

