5.6.6 Microincentives

Microincentives are increasingly being used to support users for their time and effort in using assistive applications in clinical trials and real-world settings.²⁸ Participants in the intervention arm will be provided \$0.50 each day the AiCure system is used for dosing. As participants in the control condition will not be using the AiCure system, they will be asked to track the number of steps they take each day using a fitness app on their smartphone and will be provided \$0.50 each day they send a screenshot from this app via text message to a secure research portal. Participants may also choose a different activity to track each day (e.g. number of hours they slept the night before) and text this information to the study team in the same manner. Intervention participants will be reimbursed every 2 weeks via an electronic payment system linked to the DOT Diary app (based on use of the app during that 2 week period) or receive a lump-sum payment at their next study visit.

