- b. We will use aDOT records of pill-taking over the previous 4 and 8 weeks to estimate the average number of PrEP doses per week taken by each participant, then estimate concordance of aDOT- and DBS-based indicators for protective dosing of 4-7 doses/week, with 95% confidence intervals. The DBS indicator will be defined by TFV-DP levels ≥700 fmol/punch. We will also assess concordance of aDOT- and DBS-based measures of <2, 2-3, and 4-7 doses per week, using the Kappa statistic.
- c. We will estimate concordance between an aDOT-based indicator for any PrEP use over the previous 48 hours with an indicator for detection of FTC-TP in DBS, again with 95% confidence intervals.

Margins of sampling error (MSEs). The expected sample of 240 DBS (an average of 3.59 from each of 67 participants, accounting for cumulative 20% loss to follow-up over 24 weeks) will allow us to estimate the concordance of paired binary measures within MSEs of 6.3-8.4 percentage points, depending on the sample concordance. MSEs for concordance of DOT results with detection of FTC-TP will be similar.

3. To assess the acceptability and ease of use of DOT Diary over a 24 week period

Acceptability and ease of use will be measured using the System Usability Scale (SUS) and Client Satisfaction Questionnaire (CSQ-8) adapted for use in the DOT Diary Longitudinal pilot.³⁰ Average values of our measures of acceptability and ease of use will be estimated with 95% confidence intervals.

MSEs. The estimated sample of 54 participants providing end of study data will allow us to estimate mean SUS and CSQ-8 scores within MSEs of 0.27 standard deviations (SDs).

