Client Satisfaction Questionnaire (CSQ-8) adapted for use in the DOT Diary Longitudinal pilot.²⁹ Average values of our measures of acceptability and ease of use will be estimated with 95% confidence intervals. *MSEs.* The estimated sample of 54 participants providing end of study data will allow us to estimate mean SUS and CSQ-8 scores within MSEs of 0.27 standard deviations (SDs).

Secondary Objectives

To assess PrEP coverage of sexual acts (prevention-effectiveness adherence) as measured by DOT Diary. We will estimate the probability of coverage of condomless receptive sexual acts in each period, with sexual acts treated as trials, and coverage as success. Confidence intervals will be obtained using GEE binomial models, with robust standard errors will be used to account for within-subject correlation as well as over-dispersion of the binomial outcome. *MSEs.* We also used EPIC data to estimate the average number of condomless receptive sexual acts per participant as ~7. Under this assumption, we will be able to estimate coverage probabilities within MSEs of 4-10 percentage points, depending on coverage levels and the ICC of coverage across episodes.

To evaluate the daily use of the DOT and diary components of DOT Diary through 24 weeks of follow-up. We will estimate the average use of DOT and the diary, as proportions of days and weeks on study, respectively. In the primary ITT analysis, participants will be included in the denominator through 24 weeks, regardless of dropout. In a per-protocol analysis, participants will be omitted from the denominator after dropout. *MSEs.* Proportions will be estimated within MSEs of 7-12 percentage points, depending on the sample proportions.

Subgroup analyses. Four pre-specified subgroup analyses will conducted in which interaction terms will be added to the primary GEE logistic models for protective DBS levels, to assess modification of treatment effects by 1. site; 2. age (categorized as <25 and 25+); 3. race/ethnicity, categorized as African American or Latinx vs White or other; and 4. prior PrEP use. Within-subgroup effect estimates will be presented only if the corresponding omnibus test for treatment-subgroup interaction is statistically significant at P<0.15, and results will be presented as exploratory.

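### The week-24 acceptability items go only to recent app users, so retained intervention participants who stopped before about week 12 drop out of the end-of-study SUS and CSQ-8 means, and the planned 54 makes no allowance for this

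*Protocol*

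**What the plan says.** Acceptability and ease of use over 24 weeks is the third primary objective (Protocol 2.1), measured by the SUS and CSQ-8.

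- **Collection.** Protocol 5.6.4 (Weeks 12 and 24) describes a computer-assisted interview that includes "acceptability of the app (if they used the app in the past 12 weeks"). The condition is recent use, not assigned arm.
- **Analysis.** Protocol 6.2.1, objective 3: "Average values of our measures of acceptability and ease of use will be estimated", with 95% confidence intervals. The SAP repeats this. Neither document names the time point or the analysis set in that sentence, or says how week-12 scores are used.
- **Precision.** The SAP, with the same words in Protocol 6.2.1, relies on "The estimated sample of 54 participants providing end of study data" and gives a margin of 0.27 SD. This implies a week-24 score from each person counted.
- **Non-use is foreseen.** Protocol 5.6.3: "study staff will reach out to participants by phone or text message in the event of prolonged non-use". No rate is given.
- **Denominator rule elsewhere.** For the secondary objective on app use, the SAP keeps participants in the denominator to week 24 whether or not they drop out. It gives no comparable rule for SUS and CSQ-8.

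**The concern.** Control participants never receive the app, so the interview needs some filter. A filter on recent use spares them, but at week 24 it also removes anyone in the intervention arm who still attends and has not opened the app for about 12 weeks. Continued use is plausibly related to how acceptable a person finds the app, so the filter may select on the quantity being estimated.

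At stake is what the end-of-study mean describes. A reader will take it as the view of those assigned the app and still in the study, whereas the rule yields the view of those still using it. The pilot is meant to guide refinement of the app before a larger trial (Protocol 1.0), and people who gave the app up may have the most to say about its faults.

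**Working it through.** **1. Reproduce the plan's figures.** Inputs: 67 assigned to the app (Protocol 5.3); 20% cumulative loss by week 24 (Protocol 6.2.1).

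- n = 67 × (1 − 0.20) = 53.6, rounded to 54.
- Margin = 1.96/√54 = 0.267 SD, stated as 0.27.

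Both figures reproduce. The 54 contains an allowance for loss to follow-up and nothing else, so it agrees with 5.6.4 only if every retained intervention participant used the app after about week 12.

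**2. Effect on precision.** Let q be the share of the 54 who are skipped. The documents do not give q; 10% to 40% is assumed. Respondents = 54(1 − q), and margin = 1.96/√[54(1 − q)].

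**3. Effect on the mean.** Let d be the amount, in SD, by which skipped participants would score lower than recent users. The mean in all retained is the recent-user mean minus q × d, so the recent-user mean is too high by q × d. Coverage of a nominal 95% interval for the all-retained mean is Φ(1.96 − b) − Φ(−1.96 − b), with b = q × d × √[54(1 − q)]. This takes the SD as 1 among respondents. The gap d is also assumed.

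| q (assumed) | Respondents | Margin (SD) | Bias, d = 0.25 | Coverage | Bias, d = 0.5 | Coverage |
|---|---|---|---|---|---|---|
| 10% | 48.6 | 0.281 | 0.025 | 94.7% | 0.05 | 93.6% |
| 20% | 43.2 | 0.298 | 0.05 | 93.8% | 0.10 | 89.9% |
| 30% | 37.8 | 0.319 | 0.075 | 92.5% | 0.15 | 84.8% |
| 40% | 32.4 | 0.344 | 0.10 | 91.2% | 0.20 | 79.3% |

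With d = 0 the bias is zero and coverage is 95% at every q. Coverage reaches 90% at q = 19.8% (about 11 of 54) when d = 0.5, and at q = 9.3% (about 5 of 54) when d = 1.0.

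**4. If retention is better than planned.** Protocol 4.5 sets a "retention goal of 90% at the final study assessment/visit". Then 67 × 0.90 = 60.3 are retained, with a margin of 1.96/√60.3 = 0.252 SD. Skipping 10% leaves 60.3 × 0.90 = 54.3, with a margin of 0.266 SD. The planned precision is recovered; the selection is not removed.

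**The case against.** The case against has several parts.

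- **The wording may be only a filter for controls.** Table 1 lists the acceptability items at weeks 12 and 24 with no use condition, and the programmed skip logic is not in the documents. The second point stands as a limit. But the silence of a table does not override an explicit condition in the text, and branching on arm would spare controls equally well.
- **The bar is low.** Any single use in about 12 weeks qualifies. Daily reminders (Protocol 5.6.2), staff contact after prolonged non-use (5.6.3) and $0.50 for "each day the AiCure system is used for dosing" (5.6.6) all work against complete non-use. This stands: the group is probably small, and the upper half of the assumed range is hard to square with these measures.
- **Early stoppers are heard at week 12.** Intervention participants "demonstrate taking their first dose of TDF/FTC using the app" at enrollment (5.6.2), so those who attend week 12 should meet the condition there. This also stands. A reader might infer that people who abandon the app never give acceptability scores; the documents do not support that. They are absent from the week-24 scores only.
- **Abandonment is measured in other ways.** App-use proportions are reported, and up to 24 exit interviews use "purposive sampling based on level of engagement with the app" (5.6.4). These show that people stopped, and perhaps why, but they do not supply the missing week-24 scores.
- **No decision hangs on the mean.** Objective 3 has no test, threshold or progression criterion. This stands and limits the importance of the point.

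**Conclusion.** The point holds as a mismatch between a collection rule and a planned sample. Read literally, Protocol 5.6.4 omits retained intervention participants with no app use since about week 12 from the end-of-study SUS and CSQ-8 means, while the 54 counts them.

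The loss of precision is minor: 0.28 SD at 10% skipped and 0.30 SD at 20%, against 0.27 SD. The possible bias is q × d, for example 0.05 SD at 10% skipped and 0.10 SD at 20% with a 0.5 SD gap. Both inputs are assumptions.

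A reader might infer that the acceptability result is shown to be inflated. It is not: the documents give no stopping rate and no score difference, so neither the size nor the direction of the effect is known, and the bias is zero if stoppers would score the same. Nor are the 54 and 0.27 SD miscalculated; they simply assume that nobody is skipped. The SAP's silence on time point and week-12 scores is mainly a matter for clarification rather than a separate error. The change is worth making because it is cheap and week-24 answers not asked for cannot be reliably recovered later.

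**What to change.** 1. In Protocol 5.6.4 and in the questionnaire's branching, make assignment to the intervention arm the condition for SUS and CSQ-8 at weeks 12 and 24, in place of recent use.
2. In the SAP, define the objective 3 estimate as the mean of scores collected at the week-24 visit among all retained intervention participants.
3. Show scores separately for continued and stopped users, with the number missing.
4. For those without a week-24 score, use week-12 scores, or scores taken when week 24 procedures are done at early withdrawal (Protocol 5.6.10), in a sensitivity analysis only. Some withdrawal scores will date from well before week 24 and do not belong in the main estimate.

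The cost is one branching change and two or three SAP sentences, with no new visits or instruments. The drawback is that former users rate from memory, which is why their scores should be shown apart. If the programmed questionnaire already branches on arm, only the protocol wording and the SAP text need to change.
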